#### **F tests - ANOVA: Repeated measures, between factors**

**Analysis: A priori: Compute required sample size**

**Input:**

Effect size f	= 0.5
<math>\alpha</math> err prob	= 0.05
Power (1-<math>\beta</math> err prob)	= 0.95
Number of groups	= 2
Number of measurements	= 2
Corr among rep measures	= 0.5

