### **4. Research Materials and Methods:**

The study is planned as a prospective, single-blind randomized controlled randomized study to determine the effect of acupressure on fatigue, quality of life and comfort in hemodialysis patients. This randomized controlled trial will be reported according to CONSORT guidelines and registered on ClinicalTrials.gov (23).

Patients who receive hemodialysis treatment in Adana City Hospital dialysis unit, volunteer to participate in the study and meet the research criteria, will be assigned to the study and control groups according to the days they come for dialysis treatment by lottery method (coin toss). Heads will be determined as the working group and heads will be determined as the control group. Randomization in the study will be done on the website of randomizer.org and patients will be included in the study and control groups with the appropriate randomization method according to the dialysis unit list (12,24).

**NCT Number:** 05892679

The Effect of Acupressure on Fatigue, Quality of Life and Comfort in Hemodialysis Patients. Randomized Controlled Study

The data obtained from the research will be evaluated using appropriate statistical methods. In the analysis of comparative data, parametric or nonparametric tests will be used by evaluating the conformity to the normal distribution. A package program will be used in the statistical analysis of the research.

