#### **4.1. Statistical analysis**

Demographic and patient-reported results in the study will be summarized with descriptive statistics. Continuous, normality checks of measurements will be tested with the Shapiro Wilk test. Differences in repeated measures between groups will be tested with the Repeated Measures test (repeated measure analysis of variance). Bonferroni test will be used for pairwise comparisons. Differences between groups for each measurement will be tested with the Independent Samples t-test. Number and percentage values will be given as descriptive statistics. Pearson chi-square and Fisher Exact chi-square tests will be used for differences between categorical variables. Number and percentage values will be given as descriptive statistics. P<0.05 will be taken as statistical significance.

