#### **4.2. Research Design: Prospective**

#### **4.3. Design of the Research**

The population of the research will be hemodialysis patients treated at Adana City Hospital between 30 May 2023 and 30 September 2023. The research sample will consist of patients who meet the research criteria and agree to participate voluntarily in the research. The sample number of the study was calculated using the G\*Power 3.1.9.7 program (25). In the calculation, a sample calculation was made for repeated measures ANOVA test. In the calculation, Cohen's medium effect size ( $f = 0.5$ ), 5% margin of error ( $\alpha = 0.05$ ) and 95% power ( $1-\beta = 0.95$ ) and the correlation value between repeated measurements were taken as 0.50 for each group (study and control). ) sample size was calculated as 21 patients (42 patients in total). Considering the possibility of patients leaving the groups during the research process, the number of samples for each group was increased by 30%, taking into account the possibility of data loss in order not to adversely affect the statistical power, and 30 patients (total of 60 patients) for each group (study and control) were included in the sample planned (26). Randomization in the study will be done on the website of randomizer.org and patients will be included in the study and control groups with the appropriate randomization method according to the dialysis unit list (27).

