**Output:**

Noncentrality parameter <math>\lambda</math>	= 14.000000
Critical F	= 4.0847457
Numerator df	= 1.000000
Denominator df	= 40.000000
Total sample size	= 42
Actual power	= 0.9545279

In the study, 60 hemodialysis patients were randomly assigned to the study and control groups. The study group (n=30) Acupressure is formulated according to the standards of the World Health

[figure not shown]
**NCT Number:** 05892679

Organization and in a certain order to the points of Stomach 36 (St 36), Gall Bladder 34 point (GB 34), Spleen 6 point (SP 6) and Kidney 1 point (K 1) will be applied. Consideration will be given to the appropriate pressure intensity and duration. Since the reactions of individuals will be different from each other, the stiffness and pressure will be adjusted according to the sensitivity of the individual in order not to cause tissue damage. Pressures will be applied manually by a single practitioner. Considering the anatomical area where the point is located, the most suitable thumb, index and/or middle finger will be used for application to the relevant point. Successive compressions will be applied at a frequency that does not disturb the patient, does not cause pain, and has a calming effect.

Considering the studies done, a person will be given acupressure three times a week for four weeks. No intervention will be made to the control group (n=30). In order to avoid ethical problems both groups will be given an informative training on acupressure and fatigue, increase the quality of life and comfort level in hemodialysis patients at the end of the study. The primary outcome of the study is the effect of acupuncture on fatigue in hemodialysis patients. The secondary result of the study is the effect of acupuncture on quality of life and comfort level in hemodialysis patients.

[figure not shown]
[figure not shown]
The results will be collected before the acupressure and in the 4th week of the last intervention.

Table 1. Application Points Used in the Study (33)

Application Site Name	Picture of Application Site	Description of Application Site
Stomach 36. point  (Zusanli: ST 36)		In the leg, it is one finger width lateral to the anterior crest of the tibia, and 3 cuns below the ST 35 in the depression on the lateral side of the patella.

**NCT Number:** 05892679

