## 5. Research Flow Process

The Flow Chart of this research will be completed in three stages and four steps as indicated in Figure 1.

**First Stage (Preparatory Stage):** An internationally approved acupressure certificate was obtained by the researcher in July 2022 (the certificate is in Annex I). The place where the acupressure application will be made will be arranged in accordance with the acupressure application. Necessary materials will be purchased for acupressure application (bed cover, pillow, etc.)

**Second Stage (Implementation Stage):** This stage will consist of four steps.

**In the first step:** In the first step of the application, patients who receive hemodialysis treatment in Adana City Hospital dialysis unit and meet the research criteria and are willing to participate in the research will be given brief information about the research and their verbal consent will be obtained. The fatigue experience VAS scores of the patients who accepted to participate in the study on a voluntary basis will be calculated. Those with a VAS value of fatigue severity  $\geq 4.0$  between 0 and 10 points will constitute the sample of the study.

**In the second step:** Sample selection will be completed in accordance with the inclusion, exclusion and exclusion criteria of the study, and then randomization will be performed. The patients will be informed about the purpose of the research and the research process, and the patients will be asked to fill in the "Piper Fatigue Scale", "Kidney Disease and Quality of Life Form" and "Hemodialysis Comfort Scale" as a pre-test with an informed consent form.

**Third step:** Patients in the study group will be given a total of 12 sessions of acupressure application bilaterally to Stomach 36 (St36), Gall Bladder 34 (GB34), Spleen 6 (SP6) and Kidney 1 (K1) acupuncture points for 4 weeks and 3 days a week for 20 minutes. No intervention will be made to the control group other than routine maintenance during the four-week period.

**Fourth step:** After the 4-week acupressure process is over, after the last acupressure session, the patients in the study group will have the "Piper Fatigue Scale", "Kidney Disease and Quality of Life Form" and "Hemodialysis Comfort Scale" filled face-to-face as a post-test. At the end of 4 weeks, the control group will have to fill in the "Piper Fatigue Scale", "Kidney Disease and Quality of Life Form" and "Hemodialysis Comfort Scale" as a post-test before hemodialysis.

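### The 95% power is for the group effect averaged over pre-test and post-test, not for the treatment contrast, and section 4.1 does not say which test decides fatigue

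*Combined protocol and SAP*

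**What the plan says.** - **Sample size.** Section 4.3 states that "a sample calculation was made for repeated measures ANOVA test", with f = 0.5, alpha 0.05, power 0.95 and correlation 0.50. The G*Power listing that follows is headed "F tests - ANOVA: Repeated measures, between factors". It has 2 groups and 2 measurements and returns noncentrality 14.0, critical F 4.0847457, 1 and 40 degrees of freedom, total N 42 and power 0.9545279. Enrolment is raised to 60 to allow for 30% loss.
- **Measurements.** After the G*Power output: "The results will be collected before the acupressure and in the 4th week of the last intervention". Section 5 (Research Flow Process) confirms one pre-test before the intervention and one post-test after four weeks.
- **Primary outcome.** "The primary outcome of the study is the effect of acupuncture on fatigue in hemodialysis patients". No time point or model term is attached.
- **Analysis.** Section 4.1: "Differences in repeated measures between groups will be tested with the Repeated Measures test (repeated measure analysis of variance"), then Bonferroni pairwise comparisons, then "Differences between groups for each measurement will be tested with the Independent Samples t-test". Section 4 adds that "parametric or nonparametric tests will be used by evaluating the conformity to the normal distribution". ANCOVA or a pre-test covariate appears nowhere.

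**The concern.** With one measurement before treatment and one after, the between-groups main effect is a diluted form of the treatment effect. Randomisation makes the expected pre-test difference zero, so averaging the two occasions halves whatever difference acupressure produces, and any chance imbalance at pre-test feeds into the result. The contrasts that address the trial's question are the group-by-time term (a comparison of change scores), the post-test difference, and the post-test difference adjusted for pre-test. None of these was sized.

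The open choice in section 4.1 adds to the problem. The group term, the interaction and the post-test t-test could each be reported as the primary fatigue result. They can disagree, and their power differs by an amount that depends on the pre/post correlation. Unless one is fixed in advance, the choice could be made after the data are seen.

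**Working it through.** **Reproducing the plan's figure.** For the between-factors option with m measurements, λ = f²·N·m / (1 + (m−1)ρ). With f = 0.5, N = 42, m = 2 and ρ = 0.5 (all from section 4.3 and the G*Power listing), λ = 0.25 × 42 × 2 / 1.5 = 14.0. On 1 and 40 df, critical F is 4.0847 and power 0.9545. N = 40 gives 0.945, so 42 is the smallest even N. The match confirms that the sized term is the group main effect over both occasions.

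**What f = 0.5 implies.** For two equal groups f = 0.5 is a 1.0 SD difference in the averaged score. With zero expected difference at pre-test, the post-test difference must be twice that, 2.0 SD. Let d be the post-test difference in post-test SDs and r the ratio of pre-test SD to post-test SD. Then:

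- main effect: λ = (N/4)·d² / (r² + 1 + 2ρr), df N−2
- group-by-time: λ = (N/4)·d² / (r² + 1 − 2ρr), df N−2
- post-test t-test: λ = (N/4)·d², df N−2
- ANCOVA: λ = (N/4)·d² / (1 − ρ²), df N−3

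Setting the main-effect λ to 14 at N = 42 and ρ = 0.5:

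- r = 1: 10.5·d²/3 = 14, so d = 2.00
- r = 0.8: 10.5·d²/2.44 = 14, so d = 1.80
- r = 1.2: 10.5·d²/3.64 = 14, so d = 2.20

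The documents give no SDs, so equal SDs is an assumption. The entry rule beginning "Those with a VAS value of fatigue severity" (4.0 or more on a 0 to 10 scale) could narrow the pre-test spread, which is why r below 1 is shown.

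**Power of the candidate contrasts.** The documents give no target post-test difference, so d and the range of ρ around 0.5 are assumptions. Individual randomisation, r = 1, alpha 0.05. Entries are power at N = 42 / N = 60.

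| d | ρ | Group-by-time | Post-test t-test | ANCOVA |
|---|---|---|---|---|
| 1.0 | 0.3 | 0.762 / 0.896 | 0.885 / 0.968 | 0.912 / 0.979 |
| 1.0 | 0.5 | 0.885 / 0.968 | 0.885 / 0.968 | 0.954 / 0.993 |
| 1.0 | 0.7 | 0.983 / 0.998 | 0.885 / 0.968 | 0.993 / >0.999 |
| 0.8 | 0.3 | 0.571 / 0.731 | 0.716 / 0.861 | 0.755 / 0.891 |
| 0.8 | 0.5 | 0.716 / 0.861 | 0.716 / 0.861 | 0.831 / 0.940 |
| 0.8 | 0.7 | 0.904 / 0.976 | 0.716 / 0.861 | 0.943 / 0.989 |
| 0.5 | 0.3 | 0.267 / 0.363 | 0.353 / 0.478 | 0.381 / 0.514 |
| 0.5 | 0.5 | 0.353 / 0.478 | 0.353 / 0.478 | 0.446 / 0.594 |
| 0.5 | 0.7 | 0.532 / 0.691 | 0.353 / 0.478 | 0.600 / 0.760 |

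The sized main effect, if it were read as the result, has 0.447 / 0.594 at d = 1.0 and ρ = 0.5. There λ at N = 42 is 10.5/3 = 3.5.

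Over this grid ANCOVA gains about 1 to 18 points (N = 42) or 0.1 to 16 points (N = 60) over group-by-time, and 3 to 25 or 1 to 28 points over the post-test t-test.

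**Difference detectable with 95% power at ρ = 0.5 (N = 42 / N = 60):** main effect 1.98 / 1.64 SD; group-by-time or t-test 1.14 / 0.95; ANCOVA 0.99 / 0.82.

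**Simulation check** (20,000 runs per cell). At d = 1, ρ = 0.5 and 21 per arm: main effect 0.448, interaction 0.885, t-test 0.885, ANCOVA 0.948. The ANCOVA formula runs at most about 1.4 points above simulation over the grid.

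**The case against.** - **A deciding test is implied.** Sections 4.1 and 4.3 both rest on a repeated-measures ANOVA, so it can be read as the main test with the t-tests as follow-up. That narrows the gap but does not close it: section 4.1 ranks nothing and names neither the group term nor the interaction. If the group term was meant, the sizing problem becomes worse.
- **The missing covariate is a preference, not an error.** This is largely fair. The group-by-time term uses the pre-test through change scores, and either it or the post-test t-test would cure the mismatch if pre-specified and sized. In places the ANCOVA gain is small: at d = 1, ρ = 0.3 and N = 60 it is 0.979 against 0.968 for the t-test. The covariate is a free improvement added to the correction.
- **The low powers rest on assumptions.** The 0.447 / 0.594 applies only if the main effect is taken as the result, and the values d = 0.8 and 0.5 are not in the documents. Both points stand, and the low figures at d = 0.5 do not measure an error in the plan.
- **Sixty patients may be enough anyway.** At d = 1 and ρ = 0.5 the interaction and the t-test each have 0.968 with all 60 analysed. But 60 is recruited because losses may leave 42, and there the figure is 0.885, below the stated 95%.

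None of this makes the stated 95% the power of a treatment contrast.

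**Conclusion.** The concern holds. The arithmetic behind 42 is right, but it answers a different question. The sized term reaches its stated power only for a post-test difference of about 2 SD (1.80 to 2.20 SD if the pre-test SD is 0.8 to 1.2 times the post-test SD, at ρ = 0.5), and nothing in the documents suggests that so large a difference was intended. The primary fatigue analysis is not fixed, and the pre-test covariate, which costs nothing, is unused.

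This should be corrected before outcome data are seen, but it is no ground for changing enrolment. The power figures assume individual randomisation, zero expected pre-test difference, equal SDs in the main table, and the stated ranges of d and ρ. Allocation by dialysis day, which section 4 also describes, would undermine the first assumption and is a separate point.

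**What to change.** **Section 4.1: name one primary analysis for fatigue.** Suggested text:

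> Primary analysis: ANCOVA of the post-test Piper fatigue score on group, with the pre-test Piper score as covariate, reporting the adjusted mean difference and 95% CI, for patients as allocated. This choice does not depend on the Shapiro-Wilk result. The same model is used for quality of life and comfort.

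The essential part is the single named fatigue contrast; extending the model to the secondary outcomes keeps the analyses consistent. A pre-specified group-by-time term or post-test t-test, with power computed for it, would also remove the mismatch, at lower power over the range shown. Drop the t-test at pre-test, and state that the repeated-measures group main effect is not interpreted as the treatment effect.

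**Section 4.3: replace the stated 95%** with power for the named contrast at N = 42 and N = 60. Give the post-test difference, the equal SDs and the correlation as assumptions over a range, for example d from 0.5 to 1.0 and ρ from 0.3 to 0.7. Say that the figures require individual randomisation.

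**Cost:** wording and one recalculation. The instruments, the two measurements and the 60 patients are unchanged.

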**Output:**

Noncentrality parameter <math>\lambda</math>	= 14.000000
Critical F	= 4.0847457
Numerator df	= 1.000000
Denominator df	= 40.000000
Total sample size	= 42
Actual power	= 0.9545279

In the study, 60 hemodialysis patients were randomly assigned to the study and control groups. The study group (n=30) Acupressure is formulated according to the standards of the World Health

[figure not shown]
**NCT Number:** 05892679

Organization and in a certain order to the points of Stomach 36 (St 36), Gall Bladder 34 point (GB 34), Spleen 6 point (SP 6) and Kidney 1 point (K 1) will be applied. Consideration will be given to the appropriate pressure intensity and duration. Since the reactions of individuals will be different from each other, the stiffness and pressure will be adjusted according to the sensitivity of the individual in order not to cause tissue damage. Pressures will be applied manually by a single practitioner. Considering the anatomical area where the point is located, the most suitable thumb, index and/or middle finger will be used for application to the relevant point. Successive compressions will be applied at a frequency that does not disturb the patient, does not cause pain, and has a calming effect.

Considering the studies done, a person will be given acupressure three times a week for four weeks. No intervention will be made to the control group (n=30). In order to avoid ethical problems both groups will be given an informative training on acupressure and fatigue, increase the quality of life and comfort level in hemodialysis patients at the end of the study. The primary outcome of the study is the effect of acupuncture on fatigue in hemodialysis patients. The secondary result of the study is the effect of acupuncture on quality of life and comfort level in hemodialysis patients.

[figure not shown]
[figure not shown]
The results will be collected before the acupressure and in the 4th week of the last intervention.

Table 1. Application Points Used in the Study (33)

Application Site Name	Picture of Application Site	Description of Application Site
Stomach 36. point  (Zusanli: ST 36)		In the leg, it is one finger width lateral to the anterior crest of the tibia, and 3 cuns below the ST 35 in the depression on the lateral side of the patella.

**NCT Number:** 05892679

The Effect of Acupressure on Fatigue, Quality of Life and Comfort in Hemodialysis Patients. Randomized Controlled Study

Gall Bladder 34. point (GB 34 or Yangliguan)
		
It is located on the lateral side of the leg, in the lower anterior depression of the head of the fibula.

Spleen 6. point (Sanyinjiao: SP 6)
		
It is located on the medial leg, 3 cuns above the medial malleolus, at the posterior border of the tibia.

Kidney 1. Point (K 1)
		
It is located between the 2nd and 3rd metatarsal bones on the sole of the foot (in the front of 1/3 when we divide the sole of the foot into 3 parts).

NCT Number: 05892679

The Effect of Acupressure on Fatigue, Quality of Life and Comfort in Hemodialysis Patients. Randomized Controlled Study

## 5. Research Flow Process

The Flow Chart of this research will be completed in three stages and four steps as indicated in Figure 1.

**First Stage (Preparatory Stage):** An internationally approved acupressure certificate was obtained by the researcher in July 2022 (the certificate is in Annex I). The place where the acupressure application will be made will be arranged in accordance with the acupressure application. Necessary materials will be purchased for acupressure application (bed cover, pillow, etc.)

**Second Stage (Implementation Stage):** This stage will consist of four steps.

**In the first step:** In the first step of the application, patients who receive hemodialysis treatment in Adana City Hospital dialysis unit and meet the research criteria and are willing to participate in the research will be given brief information about the research and their verbal consent will be obtained. The fatigue experience VAS scores of the patients who accepted to participate in the study on a voluntary basis will be calculated. Those with a VAS value of fatigue severity  $\geq 4.0$  between 0 and 10 points will constitute the sample of the study.

**In the second step:** Sample selection will be completed in accordance with the inclusion, exclusion and exclusion criteria of the study, and then randomization will be performed. The patients will be informed about the purpose of the research and the research process, and the patients will be asked to fill in the "Piper Fatigue Scale", "Kidney Disease and Quality of Life Form" and "Hemodialysis Comfort Scale" as a pre-test with an informed consent form.

**Third step:** Patients in the study group will be given a total of 12 sessions of acupressure application bilaterally to Stomach 36 (St36), Gall Bladder 34 (GB34), Spleen 6 (SP6) and Kidney 1 (K1) acupuncture points for 4 weeks and 3 days a week for 20 minutes. No intervention will be made to the control group other than routine maintenance during the four-week period.

**Fourth step:** After the 4-week acupressure process is over, after the last acupressure session, the patients in the study group will have the "Piper Fatigue Scale", "Kidney Disease and Quality of Life Form" and "Hemodialysis Comfort Scale" filled face-to-face as a post-test. At the end of 4 weeks, the control group will have to fill in the "Piper Fatigue Scale", "Kidney Disease and Quality of Life Form" and "Hemodialysis Comfort Scale" as a post-test before hemodialysis.

**Third Stage (Reporting Stage):** At this stage Statistical analysis of the data obtained from the patients will be made and a research report will be written.

**NCT Number:** 05892679

The Effect of Acupressure on Fatigue, Quality of Life and Comfort in Hemodialysis Patients. Randomized Controlled Study

**Figure 1.** Flow Chart of the Research

STAGE 1. PREPARATION STAGE	
Arrangement of Adana City Hospital dialysis unit in accordance with acupressure application in order to perform acupressure application.
		
STAGE 2 IMPLEMENTATION PHASE	1. Step	
Contacting patients receiving hemodialysis treatment in Adana City Hospital dialysis unit, Determining compliance with the criteria, Measuring fatigue experience VAS scores, Recruiting patients willing to participate in the study
	
	2. Step	
Determining the sample according to the criteria Performing the randomization (Study Group; n=30 - Control Group; n=30) Getting Informed Consent and pre-test data collection forms ("Patient Description Form", "Piper Fatigue Scale", "Kidney Disease and Quality of Life Form" and "Hemodialysis Comfort Scale")
	
	3. Step	
Making acupressure group (n=30) apply acupressure for 20 minutes three times a week for four weeks.
	
No intervention in the control group (n=30)

	4. Step	
Having the study group (n=30) fill out the post-test data collection forms ("Piper Fatigue Scale", "Kidney Disease and Quality of Life Form" and "Hemodialysis Comfort Scale") after the last acupressure session, after the 4-week acupressure process is over.
	
The control group to be fill out the post-test data collection forms ("Piper Fatigue Scale", "Kidney Disease and Quality of Life Form" and "Hemodialysis Comfort Scale") at the end of the interview at the end of 4 weeks.

STAGE 3 REPORTING PHASE	
ANALYSIS OF DATA AND WRITTEN RESEARCH REPORT
		

**NCT Number:** 05892679

The Effect of Acupressure on Fatigue, Quality of Life and Comfort in Hemodialysis Patients. Randomized Controlled Study

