### 5.1. Data Collection Form

In the study, data will be collected with a data collection form consisting of four parts: "Patient Description Form", "Piper Fatigue Scale", "Kidney Disease and Quality of Life Form (KDQOLTM-36)" and "Hemodialysis Comfort Scale".

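### The screening fatigue VAS is, in the stated order, the only fatigue score taken before randomisation, yet the plan gives it no role after entry; it should be kept, reported by arm and prespecified as a covariate

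*Combined protocol and SAP*

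**What the plan says.** **Entry.** Section 5, First step: "The fatigue experience VAS scores of the patients who accepted to participate in the study on a voluntary basis will be calculated". Patients at 4.0 or above on the 0 to 10 scale "between 0 and 10 points will constitute the sample of the study". Figure 1 places the same measurement in Step 1 ("Measuring fatigue experience VAS scores") and nowhere else.

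**Order of randomisation and pre-test.** In the Second step, sample selection is completed "and then randomization will be performed". Patients are then informed and complete the Piper, quality of life and comfort scales "as a pre-test with an informed consent form". Figure 1, Step 2 keeps that order: randomisation, then "Getting Informed Consent and pre-test data collection forms". The VAS is not one of the pre-test forms listed there.

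**Data form.** Section 5.1: "data will be collected with a data collection form consisting of four parts". The parts named are a patient description form, the Piper scale, the KDQOL-36 and the comfort scale.

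**Post-test.** The Fourth step and Figure 1, Step 4 list the Piper, quality of life and comfort scales for both arms, without the VAS.

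**Outcome and analysis.** The outcome statement, below the G*Power output in 4.3, reads "The primary outcome of the study is the effect of acupuncture on fatigue in hemodialysis patients" (the word acupuncture is the document's) and names no instrument. The Piper scale is the only fatigue scale scheduled both before and after treatment. Section 4.1 plans repeated measures ANOVA and an independent-samples t-test at each measurement. It names no scale, no covariate and no stratification factor. It does promise descriptive statistics for patient-reported results in general.

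**The concern.** Fatigue is the primary outcome and the control arm receives no intervention. Section 4 calls the trial single-blind without saying who is blinded, and no sham is described. If the pre-test is completed in the order listed, patients may already know their arm when they first fill in the Piper scale. That pre-test enters the planned repeated measures ANOVA, and the between-factors test used for the sample size averages it with the post-test.

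The screening VAS does not have this weakness. Since it is an entry condition, every randomised patient should have a value. As planned, it is used once as a gate and then has no stated function. Two things are at stake: a check of baseline fatigue severity by arm on a score that allocation could not have moved, and some precision in the post-test comparison with 30 patients per arm. A further consequence is that no change or treatment effect can be reported on the scale by which patients were selected.

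**Working it through.** **1. Plan's own figure.** Inputs from the G*Power listing in 4.3: f = 0.5, alpha = 0.05, 2 groups, m = 2 measurements, rho = 0.5, N = 42.
- lambda = N × f² × m / (1 + (m − 1) × rho) = 42 × 0.25 × 2 / 1.5 = 14.0
- With 1 and 40 degrees of freedom, critical F = 4.0847 and power = 0.9545.
- N = 40 gives 0.945, so 42 is the smallest even total reaching 0.95.

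The stated figures reproduce exactly, and nothing below alters them.

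**2. Where each fatigue measure stands.**

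| Point in the plan | VAS | Piper |
|---|---|---|
| First step, before randomisation | yes | no |
| Second step, listed after randomisation | no | yes |
| Named part of data form (5.1) | no | yes |
| Fourth step, post-test | no | yes |
| Named in 4.1 | no | no |

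**3. VAS as the only covariate for post-test Piper.** The correlation r between screening VAS and post-test Piper is not in the documents; 0.3 to 0.5 is assumed. Residual variance is 1 − r², and the equivalent sample-size factor is 1 / (1 − r²).
- r = 0.3: 1 − 0.09 = 0.91; factor 1.10 (60 patients act like 60 / 0.91 = 66)
- r = 0.5: 1 − 0.25 = 0.75; factor 1.33 (60 / 0.75 = 80)

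As an illustration on the power scale, carry a standardised difference of 1.0 (2 × f) to the post-test alone, with N = 42. ANCOVA power is 0.885 if the covariate explains nothing, 0.912 at r = 0.3 and 0.954 at r = 0.5.

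**4. VAS added to an ANCOVA that already has the Piper pre-test.** Let a = 0.5 be the Piper pre-post correlation (the plan's value, 4.3), r the VAS to post-test correlation (assumed), and c the VAS to Piper pre-test correlation (assumed 0.4 to 0.6).

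R² = (a² + r² − 2·a·r·c) / (1 − c²). The Piper pre-test alone leaves 1 − 0.25 = 0.75 of the variance, so the added factor is 0.75 / (1 − R²).

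| r | c | R² | 1 − R² | Added factor |
|---|---|---|---|---|
| 0.3 | 0.4 | (0.34 − 0.12) / 0.84 = 0.262 | 0.738 | 1.016 |
| 0.3 | 0.6 | (0.34 − 0.18) / 0.64 = 0.250 | 0.750 | 1.000 |
| 0.5 | 0.4 | (0.50 − 0.20) / 0.84 = 0.357 | 0.643 | 1.167 |
| 0.5 | 0.6 | (0.50 − 0.30) / 0.64 = 0.3125 | 0.6875 | 1.091 |

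The added gain is therefore about 0-2% at r = 0.3 and 9-17% at r = 0.5. The upper case assumes that a single-item screen predicts the post-test as well as the plan takes the Piper pre-test to do. Enrolling only patients at 4.0 or above narrows the VAS range, which tends to lower r.

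**The case against.** The strongest reply is that no error is shown. Screening on a short scale and measuring the outcome on a fuller one is ordinary design, and the Piper scale has both a pre-test and a post-test. That stands in full.

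Three stronger readings are tempting, and the documents do not support them:
- *No result at all can be given on the VAS.* The general sentence on descriptive statistics in 4.1 allows a baseline summary by arm. Only post-treatment results are impossible.
- *The VAS was deliberately left out of the record and the analysis.* Section 5.1 names four parts, but the items of the patient description form are not shown, and the VAS could be recorded there. Section 4.1 names no scale, not even Piper, so its silence is not a decision to exclude.
- *The trial should report how many patients fall below 4.0.* Nothing in the documents makes 4.0 more than an entry value. Patients selected at or above it will partly drift below by regression to the mean, and dichotomising discards information.

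It can also be said that the direct remedy is to take the Piper pre-test before randomisation. That is fair, and most of the case for the VAS covariate would then go. As the plan is written, however, the pre-test is listed after allocation. The VAS is already collected, and section 4.1 commits to no adjustment of any kind.

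**Conclusion.** The point holds as a modest, nearly free improvement. In the order given in section 5 and Figure 1, the VAS is the one fatigue score that cannot be affected by allocation, and the plan assigns it no role beyond entry. Its value as a baseline check does not depend on any assumed correlation.

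The precision gain does. It is about 10% to 33% in equivalent sample size if the VAS is the sole covariate with r between 0.3 and 0.5. It is about 0-2% to 9-17% once the Piper pre-test is in the model, under the correlations assumed above, and range restriction may reduce it further. The larger figures should not be read as the expected gain over a model that already uses the Piper pre-test.

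The conclusion rests on the listed sequence being the actual one. Section 4 also speaks of assigning patients by dialysis day with a coin toss. If days were allocated before screening, the VAS would lose its advantage.

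**What to change.** 1. In 5.1, state where the screening VAS is recorded and that the value is retained in the study data for every randomised patient.
2. In 4.1, add the screening VAS to the baseline table by arm, as a description without a significance test.
3. In 4.1, prespecify the between-arm comparison of post-test Piper fatigue as an ANCOVA with the screening VAS as a continuous covariate, and say whether the Piper pre-test is also in the model. If the pre-test stays after randomisation, give that as the reason for using the VAS.
4. Optionally, repeat the VAS at post-test in both arms and report the between-arm difference as supportive only. Do not make the number below 4.0 a headline result.

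Items 1 to 3 need no new measurement; they cost one recorded field, one table row and one degree of freedom. Item 4 adds a single-item scale at a visit already planned and one further outcome, to be labelled supportive. The sample size does not change, and Piper remains the fatigue outcome measure.
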